### **9.1 Incidents**

A Study Incident is defined as any problem involving any of the study devices, reference methods, procedures, equipment, and human subjects as a result of execution of this protocol. Study Incidents may adversely (or potentially adversely) affect human safety, the integrity of the evaluation data, and/or the operation of devices or systems. Any incident which affects the health, safety, and welfare of human subjects will be reported as an Adverse Event (AE) (See [Section 11](#)). In the event an Incident results in an injury to a Study RN, the incident will be evaluated by the Investigator to determine the severity (mild, moderate, severe) and relationship to B. Braun PA (none, unlikely, possible, probable, or definite).

Examples of Study Incidents that are not AEs may be mislabeling or adulteration of the investigational device, device malfunctions that do not contribute to or cause an AE, or damage to devices caused by shipping or handling. Device malfunctions are defined as failure of an investigational medical device to perform in accordance with its intended purpose when used in accordance with the instructions for use or clinical investigational protocol. Incidents resulting in an AE or protocol deviation will be documented in the EDC.

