## 11 ADVERSE EVENTS AND SERIOUS ADVERSE EVENTS

### 11.1 Adverse Events

Study safety will be evaluated by assessment of AEs.

The Study RNs in this study are subjected to minimal health risk from the use of the devices and are anticipated to be experienced users of PIVC devices. The subjects enrolled in this study may be exposed to the standard health risks associated with PIVC insertion. All events

related to both the standard-of-care products used in the hospital and the B. Braun PA and any required procedures will be evaluated for determination as AEs and documented on the eCRFs.

An AE is any untoward medical occurrence, unintended disease or injury or any untoward clinical signs (including an abnormal laboratory finding) in subjects, users or other persons, whether or not related to the investigational device. AEs may include, but are not limited to, premature device removal, minor and major complications, infection, thrombophlebitis, accidental needlestick injuries, and device failures (i.e., disconnection, twisted port hub, leakage, or failure of safety feature). AE collection for each subject will begin after the ICF is signed and will continue until the completion of all study procedures or until the subject withdraws consent or is withdrawn from the study.

AEs will be reported by the Investigator and the Sponsor will use the reported AE term to determine the MedDRA system organ class and preferred term. The investigator will also report the AE severity (mild, moderate, severe) and relationship of the AE to either the standard-of-care products used in the hospital or the B. Braun PA.

No exposure hazard is expected. The investigational devices were manufactured according to Good Manufacturing Practices (GMPs).

Specific guidelines for classifying AEs by intensity are provided in [Table 3](#).

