### **12.3 Safety Analyses**

Adverse events will be summarized as an overall incidence of at least one event, incidence within system organ class only, and incidence by system organ class and preferred term. Events may include, but are not limited to: minor and major complications, infection, thrombus, phlebitis, accidental needle sticks, and device failures (i.e., disconnection, twisted port hub, leakage, and failure of the safety feature). [Section 11](#) of this protocol details AE definitions and relationship classifications.

A Statistical Analysis Plan (SAP) will be prepared after the protocol and eCRF are approved. This document will provide further details regarding the definition of analysis variables and analysis methodology to address all study objectives. The SAP will serve as a complement to the protocol and supersedes it in the case of any differences.

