## 9.5. Safety Analyses

### 9.5.1. Adverse Events

For adverse event (AE) analyses, summary tables and/or listings will be provided for all AEs and severe adverse events (SAEs), respectively, in terms of event category by MedDRA coding for Stage 1 and Stage 4. In addition, both AEs and SAEs, respectively, will be summarized for Stage 1 and Stage 4 in terms of relationship to the procedure, to the device, and severity. Except where indicated, if a subject reports the same AE more than once, or reports the same AE on multiple occasions, the most severe AE will be presented when calculating the number and percentage of subjects with that particular event. AE outcomes will be assessed descriptively.

A descriptive line listing of each AE by subject also will be provided.

All safety analysis will be based on MITT Population, which includes only subjects in whom a procedure is attempted after enrollment.

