## **15. DATA LISTINGS TO BE GENERATED**

Listing 15.1 Individual Patient Demographics -ITT Population

Listing 15.2 Individual Patient Incidents -MITT Population

Listing 15.3 Device -MITT Population

Listing 15.4 Adverse Events -MITT Population

Listing 15.5 Protocol Deviation -MITT Population

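### Study nurse injuries count as adverse events under the protocol but have no place in the SAP's safety outputs, and two protocol rules for rating their cause conflict

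*SAP*

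**What the plan says.** Protocol 11.1 defines an adverse event as an occurrence "in subjects, users or other persons, whether or not related to the investigational device". Its examples include needlesticks: "AEs may include, but are not limited to, premature device removal, minor and major complications, infection, thrombophlebitis, accidental needlestick injuries". Protocol 12.3 repeats them among the events to be summarised ("thrombus, phlebitis, accidental needle sticks, and device failures"), and so does the Safety Analyses row of the SAP synopsis. Protocol 3.2 and the opening of Protocol 12 both say that data from participating nurses will be part of the safety analysis.

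The SAP takes a narrower line. Section 9.5.1 says: "All safety analysis will be based on MITT Population, which includes only subjects in whom a procedure is attempted after enrollment". The incident listing in SAP Section 15 is titled "Listing 15.2 Individual Patient Incidents -MITT Population". SAP Section 10 reports no departure from the protocol's analyses. It adds that the study ended before Stage 2, so Stage 4 analyses will not be done.

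On causality, Protocol 9.1 says that when an incident injures a Study RN, "the incident will be evaluated by the Investigator to determine the severity (mild, moderate, severe) and relationship to B. Braun PA". Protocol 11.1 has the investigator rate each adverse event against either the hospital's standard-of-care products or B. Braun PA.

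**The concern.** A needlestick during catheter insertion mainly threatens the person holding the needle. If the protocol counts such events and promises to analyse them, but the SAP's safety population contains only patients, the outcome is dropped by the written rule and not merely left undescribed. The SAP synopsis lists needle sticks as possible events. A reader who sees that list, and then sees none in the tables, could take the absence as reassurance when nurses were never in the population summarised.

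The causality rule adds to the problem. The only rule that names Study RN injuries points to a product that nurses were not using in the one stage that produced clinical data. Two investigators could rate the same Stage 1 needlestick differently, depending on which section they followed.

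**Working it through.** No arithmetic applies, so the check sets the passages against each other.

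1. **Are nurse injuries meant to be analysed?** Protocol 11.1 covers users, and Protocol 3.1 makes Study RNs responsible for insertions. Protocol 9.1 provides expressly for an injury to a Study RN. Protocol 3.2 and 12 bring nurses' data into the safety analysis. The needlestick lists do not say whose injury is meant. That it is chiefly the nurse's is an inference from these sections, and a strong one.

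2. **Can a nurse belong to the safety population?** SAP 8.1 builds ITT from consented, eligible, enrolled subjects, and MITT from ITT subjects in whom a PIVC was attempted. A nurse makes the attempt and is not its subject. No nurse qualifies.

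3. **Which outputs could hold the event?** The planned safety outputs are Tables 14.6.1 and 14.6.2, Listings 15.2 (incidents) and 15.4 (adverse events), and Figure 16.2 (onset of adverse events): 2 + 2 + 1 = 5. All five are labelled MITT. So is the device listing, 15.3.

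4. **Is there another route?** The SAP defines no RN population. Table 14.2.1 summarises nurse demographics under the ITT label, but ITT is defined on patients. Protocol 11.1 times adverse event collection from each subject's consent, and the adverse event row of Protocol Table 2 sits under the subjects block. The promise in Protocol 12 does not rescue the analysis, because Protocol 12.3 gives the SAP precedence.

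5. **Which causality rule applies in Stage 1?**
   - Protocol 9.1: Study RN injuries, rated against B. Braun PA only.
   - Protocol 11.1: all adverse events, including those in users, rated against the standard-of-care products or B. Braun PA. The category definitions that follow, however, speak of the study device.
   - Protocol 11.4: reportable needlestick events with either set of products.
   - SAP 9.5.1: relationship to the procedure and to the device, by stage, with no restriction to B. Braun PA.

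   Protocol 6.1 has nurses use the institution's own product in Stage 1. Under 9.1 a Stage 1 injury is judged against a product that was not in use. Under 11.1 it is judged against the one that was. The two passages conflict.

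6. **Can the size be put in numbers?** No. The documents give neither the number of Stage 1 attempts achieved nor the number of nurse injuries. The planned minimum of 316 successful placements cannot stand in for exposure in a study stopped for recruitment futility.

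**The case against.** The best reply is that this is a reporting gap of modest consequence. Needlestick rate is neither an objective nor an endpoint, and Protocol 11.1 describes the risk to nurses as minimal. With Stage 4 cancelled, no comparison between products is possible. Incidents go into the eCRF under Protocol 9, and Protocol 11.3 and 11.4 provide for individual reports of device effects, malfunctions and reportable needlesticks. A needlestick during an MITT patient's insertion might also be logged under that patient and so reach a listing.

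Most of this limits the importance without removing the gap. Individual reports do not replace the summary that the protocol promises. The documents do not say that a nurse's injury is to be logged under the patient. Doing so would present it as a patient's event with patients as the denominator.

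The objection does defeat several stronger readings that a reader might infer:

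- **That the SAP itself rates nurse injuries only against B. Braun PA.** That rule is in Protocol 9.1. SAP 9.5.1 has no such limit.
- **That Stage 1 injuries have no valid causality rating.** Protocol 11.1 supplies one against the standard-of-care products, and 11.4 covers those products for needlestick reporting. The defect is two inconsistent rules.
- **That the report would state zero needlesticks.** A table headed MITT is silent on nurses and asserts nothing about their count.
- **That the planned sample size bounds the injury rate.** No achieved count is given, so no such bound is available.

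**Conclusion.** The point holds in two parts. First, the protocol includes injuries to users and nurses' data in the safety analysis. The SAP confines that analysis to patients, in all five planned safety outputs, and declares no change. A Study RN injury has no planned table, denominator or listing. Second, Protocol 9.1 and 11.1 give inconsistent rules for rating the cause of such an injury, and the inconsistency matters because the only clinical data come from Stage 1.

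This rests on reading users to include Study RNs, which Protocol 9.1 supports, and on nurse injuries not being entered under a patient's record, on which the documents are silent. The primary endpoint is unaffected. How many injuries are involved is unknown. The change should be made because a safety outcome that the protocol names would otherwise go unreported, and the data needed should already be in the eCRF.

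**What to change.** In SAP 9.5.1, define a Study RN safety set. Report RN injuries, needlestick and other, for Stage 1 as a count over the number of insertion attempts actually recorded, in one small table. Extend Listing 15.2 to cover RN incidents as well as patient incidents. Reconcile Protocol 9.1 with 11.1, and report the relationship of each Stage 1 RN injury to the product in use, in line with 11.1. If the sponsor prefers to keep safety reporting to patients only, SAP Section 10 should say that this departs from the protocol.

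The cost is SAP wording, one extra table and a wider listing. Protocol 9 already sends incidents to the eCRF, and Protocol 6.1 does the same for insertion attempts, so no new collection should be needed. The downside is that some Stage 1 relationship ratings made under Protocol 9.1 may have to be re-queried with the sites.

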## 9.6. Medications

Only medications that are used in the treatment of a patient AE/SAE will be collected and coded. Each medication will be coded to a preferred term and an anatomic therapeutic classification (ATC) code using the WHO Drug Dictionary. The number and percentage of patients taking each medication will be summarized by medication class (anatomical classification) and preferred term.

## 9.7. Medical History

Medical history data will not be collected for this study.

## 10. CHANGES TO ANALYSES PLANNED IN THE PROTOCOL

There were no changes to the analyses planned in the protocol version 1.0 Amendment 1. However, due recruitment futility, this study was terminated prior to reaching Stage 2. Therefore, all analyses related to Stage 4 will not be performed.

## 11. REVISION HISTORY

Date	Version	Revised By	Reason for Revision
March 8, 2021	1.0	N/A	This is the first version of this document.
September 15, 2021	2.0	1.0	The study was terminated early due to recruitment futility.
December 3, 2021	3.0	2.0	Additional endpoint analysis

## 13. PROGRAMMING SPECIFICATIONS

The rules for programming derivations and dataset specifications will be provided in separate documents.

## 14. STATISTICAL TABLES TO BE GENERATED

Table 14.1 Patient Disposition -ITT Population

Table 14.2.1 Demographics for Nurses - ITT Population

Table 14.2.2 Demographics and Patient Characteristics - ITT Population

Table 14.3 Summary of Daily Catheter Examination - MITT Population

Table 14.4.1 Summary of Primary Endpoint Analysis - MITT Population

Table 14.4.2 Summary of Primary Endpoint Analysis - PP Population

Table 14.5.1 Summary of Secondary Endpoint Analysis -MITT Population

Table 14.5.2 Summary of Secondary Efficacy Endpoint Analysis – Median Indwell time for Catheters -MITT Population

Table 14.5.3 Summary of Secondary Efficacy Endpoint Analysis – Median Indwell time for Catheters Subgroup Analysis - MITT Population

Table 14.6.1 Summary of Adverse Events -MITT Population

Table 14.6.2 Summary of Device and Procedure Related Adverse Events - MITT Population

## **15. DATA LISTINGS TO BE GENERATED**

Listing 15.1 Individual Patient Demographics -ITT Population

Listing 15.2 Individual Patient Incidents -MITT Population

Listing 15.3 Device -MITT Population

Listing 15.4 Adverse Events -MITT Population

Listing 15.5 Protocol Deviation -MITT Population

## **16. FIGURES TO BE GENERATED**

Figure 16.1 Summary of Kaplan-Meier of onset of complication

– MITT Population

Figure 16.2 Summary of Kaplan-Meier of onset of Adverse Events

– MITT Population
